than for mania. On the LIFE PSR, our eligible population will score at the higher end of the subthreshold range (3-4) as those scoring 5-6 will confer research diagnostic criteria and therefore not meet the inclusion criteria for the trial; based on our pilot trial (mean baseline BDI-II score of 37.9), participants will tend to be towards the upper end of the subthreshold range (i.e. mean around 3.75). Button [81] reported that a MCID for the BDI-II is around 17-18%; given that we expected similar sensitivity for the mean LIFE depression PSR scores as would be the case for BDI-II, a difference of around 0.5 points (0.18*[3.75-1]=0.50 (to 2 d.p.)] on the PSR for LIFE depression in order to indicate that CBT_{BAR} is having an important effect.

To detect a between-group mean difference of 0.5 points (SD=1.3 points [80]) on the mean 4-week PSR for LIFE depression score at 27-weeks follow-up we require 286 participants with outcome data to achieve 90% power, using an ANCOVA (with 2.5% two-sided significance level), assuming a conservative correlation of 0.4 between baseline and 27-week scores [82]. Inflating the sample size to allow for a conservative 15% attrition (attrition was 13% in our feasibility trial, 57) requires a target to randomise of 338 participants (approx. 68 per site). This sample size will provide greater than 90% power to detect a rather more conservative MID on LIFE PSR for mania (e.g. equating to 98.5% to detect a target effect of 0.25 points [estimated within-group SD=0.5 points]) [80]. In each case, power will be increased due to the (multiple) correlation between outcome and the full set of explanatory variables adjusted for in the model. We have not allowed for a random therapist effect in our sample size calculation as the effect on depression outcome (BDI-II) in our pilot trial was 0, although the confidence interval was wide; we will, however, include the addition of a random therapist effect amongst our sensitivity analyses.

Assuming a standardised effect size of the intervention on the HAPPI of 0.4, 286 participants with mediator and primary outcome data will also allow for 88.5% power for estimation of an indirect effect of 40% via the putative primary mediator (HAPPI), or 83.5% power for the estimation of a 30% indirect effect, based on a total effect on the intervention of the MCID (i.e. 0.5) (with a 2.5% significance level, estimated using the R package medssp, based functions provided in Vittinghoff and Neilands [83]

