8. STATISTICS & DATA ANALYSIS

MAIN TRIAL DATA ANALYSIS

All comparative analyses will be 'as randomised', where participants are analysed according to the group they were randomised to, regardless of what treatment they received. Complete details of analyses will be included in a Statistical Analysis Plan which will be finalised and approved by the Trial Steering Committee prior to database lock and prior to any analysis.

Co-primary outcomes

The primary analyses for each of the co-primary outcomes (mean 4-week PSR for LIFE depression score and for LIFE mania score at 27-week follow-up) will use ANCOVA, with adjustment for the stratification factors (site and BAR group) and the baseline PSRs for depression and mania and prior CBT (yes/no). Missing data will be explored; for each co-primary, if less than 15% are missing, and less than 10% differential missing data, then case analysis (CCA) will be used, otherwise it will be multiple imputation by chained equations (MICE) [94] assuming that the data are 'missing at random'. Tests will use a 2.5% significance level and two-sided 97.5% confidence intervals (CIs) will be presented.

Moderator: We will explore BAR group (I, II or II) and prior CBT (yes; no) as potential moderators by adding interactions with treatment arm to the primary outcome models.

Mechanisms: We will evaluate this using causal inference methods for mediation [95] using an instrumental variables approach (via two-stage least squares) to estimate the indirect effect of CBT_{BAR} on each of LIFE mania and LIFE depression scores via the HAPPI total score at the preceding time-point (e.g. 17-week HAPPI for 27-week LIFE scores). The more complex causal model incorporating BC and ISS will be investigated using structural equation modelling. As a post-randomisation effect modifier, the impact of the number of CBT_{BAR} sessions attended will be assessed using principal stratification methods; other measures of intervention receipt, including antidepressant medication, will be considered in separate analyses.

Secondary outcomes

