Secondary outcome measures (including the primary outcome measures at time-points other than 27-week) will be analysed using generalised linear models, with link function appropriate to the type of data, adjusted for stratification factors and the baseline value of the outcome measure (where applicable).Time to events (transition to first episode (hypo)mania and recovery from BAR symptoms) will be analysed using a Cox proportional hazards model, adjusted for stratification factors. Tests will use a 5% significance level and two-sided 95% CIs will be presented.

Sensitivity analysis

The alternative method to that used in the primary analysis will be used as a sensitivity analysis (MICE if CCA, or vice versa). Sensitivity analyses will also include the addition of a random therapist effect in a partially-nested model (clustering by therapist in the CBT_{BAR} + TAU arm but no clustering in the TAU arm). A further sensitivity analysis will use longitudinal mixed-effects model incorporating all follow-up time-points (as factors), fitted using maximum likelihood, accommodating the within-participant correlation over time with an unstructured covariance matrix and including stratification factors and the baseline PSRs for depression and mania as covariates.

QUALITATIVE ANALYSIS

Data will be analysed using thematic analysis [96], which provides an accessible and flexible approach, resulting in a rich account of qualitative data. The data generation and analysis will be conducted with leadership and ongoing involvement from individuals with personal experience of the provision of the receipt of this treatment and/or the experience of BAR mood experiences. This involvement is expected to enhance the study during the conduct and analysis of all interviews. We will take a critical realist position, and data will be coded at a manifest level (i.e., analysing only the immediate meaning of participants' language) to produce an accessible body of coded data from which meaningful thematic representations of participants' perspectives can be reported. All semi-structured interviews will be transcribed verbatim and coded systematically and iteratively within NVivo qualitative data analysis software (Version 11, 2016).

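### The same LIFE PSR scores are adjusted for three different covariate sets, with no reason given; using one set costs nothing and sharpens the 52-week and mixed-model results slightly

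*Protocol*

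**What the plan says.** All three covariate sets are in Protocol section 8.

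- **27-week PSR (Co-primary outcomes).** ANCOVA with "adjustment for the stratification factors (site and BAR group) and the baseline PSRs for depression and mania and prior CBT (yes/no".
- **PSR at weeks 17 and 52 (Secondary outcomes).** The rule covers these scores by name: "Secondary outcome measures (including the primary outcome measures at time-points other than 27-week) will be analysed using generalised linear models". The models are "adjusted for stratification factors and the baseline value of the outcome measure (where applicable".
- **All visits together (Sensitivity analysis).** A "longitudinal mixed-effects model incorporating all follow-up time-points (as factors), fitted using maximum likelihood", "including stratification factors and the baseline PSRs for depression and mania as covariates".

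| Analysis of LIFE PSR | Site, BAR group | Own baseline PSR | Other pole's baseline PSR | Prior CBT |
|---|---|---|---|---|
| 27-week ANCOVA | yes | yes | yes | yes |
| Weeks 17 and 52 | yes | yes | no | no |
| Longitudinal mixed model | yes | yes | yes | no |

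Two other sensitivity analyses sit beside the mixed model. One swaps the missing-data method: "The alternative method to that used in the primary analysis will be used as a sensitivity analysis (MICE if CCA, or vice versa". The other adds a random therapist effect. Neither states a change of covariates.

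**The concern.** The protocol spells out each set, so this is a stated rule and not a detail left to the SAP. An SAP that follows the protocol would inherit the mismatch.

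The fuller set is the one the protocol itself favours. Section 3 (Sample size: quantitative work) expects power to rise because of the covariates in the model beyond the outcome's own baseline. Section 8 uses prior CBT as a covariate and proposes to explore it as a moderator.

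Three things are at stake, all small:

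- Efficacy aim 2 and hypothesis 1b ask whether the benefit lasts to 52 weeks, so readers will set the 52-week estimate beside the 27-week one. As planned, the two differ in adjustment as well as in time.
- A sensitivity analysis is clearest when it changes one thing. The mixed model changes how the visits and incomplete data are used, and it also drops a covariate.
- The 52-week model leaves unused two baseline variables that the 27-week analysis already requires.

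**Working it through.** **Inputs.** From Protocol section 3 (Sample size: quantitative work): difference 0.5 points, SD 1.3, baseline correlation r = 0.4, two-sided 2.5% level, 286 with outcome data, 15% attrition, 338 randomised. From section 8 (Secondary outcomes): two-sided 5% level for the PSR at other time-points. The protocol gives no figure for the variance explained by the other baseline PSR and prior CBT, so a range is assumed.

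**1. The plan's own figure.**

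- n per arm = 2 × (2.241 + 1.282)² × 1.3² × (1 − 0.4²) / 0.5² = 2 × 12.41 × 1.4196 / 0.25 ≈ 141, or 282 in total against the stated 286.
- At 143 per arm, power is 90.4% (normal approximation).
- 286 / 0.85 = 336.5, so 337, or 338 as an even total.

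The figure reproduces using the outcome's own baseline alone. The 52-week model keeps that covariate, so the mismatch does not touch the sample size.

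**2. Precision at 52 weeks.** Assume that 286 analysed, SD 1.3 and r = 0.4 carry over from 27 weeks. Let R² be the share of the remaining residual variance explained by the two omitted covariates.

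- SE = 1.3 × √0.84 × √(2/143) × √(1 − R²) = 0.1409 × √(1 − R²)
- Power = Φ(0.5/SE − 1.96)

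| Assumed R² | √(1 − R²) | SE | Power, two-sided 5% |
|---|---|---|---|
| 0 (as planned) | 1 | 0.1409 | 94.4% |
| 0.02 | 0.990 | 0.1395 | 94.8% |
| 0.05 | 0.975 | 0.1373 | 95.4% |
| 0.08 | 0.959 | 0.1352 | 95.9% |

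Over 2% to 8%, the planned SE is about 1% to 4% larger than it need be (1/0.990 to 1/0.959). If the added share is instead expressed on total variance, values of 0.02, 0.05 and 0.10 give power of 94.9%, 95.5% and 96.6%. The larger figures reflect the different scale and the wider range.

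**3. Bias or noise?** In 4,000 simulated trials per setting (286 participants, complete data, true difference 0.5), the mean estimates with and without the extra covariate were:

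- added share of total variance 0.02: 0.5038 and 0.5035
- 0.05: 0.4987 and 0.4982
- 0.10: 0.5007 and 0.5002

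They agree to within 0.001, so there is no bias. Within a single trial the two estimates differed by chance, with SD 0.023, 0.035 and 0.049 points, against an SE of about 0.13 to 0.14. A hand check agrees: 1.3 × √share × √(2/143) = 0.022, 0.034 and 0.049. These figures describe a covariate change of the assumed strength. For the mixed model only prior CBT is missing, so only its share counts.

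**4. Missing data in the mixed model.** Maximum likelihood relies on missingness being explained by what the model holds. If prior CBT predicts dropout, and also outcome beyond the other covariates, then leaving it out changes that condition relative to the ANCOVA. The protocol gives no evidence either way.

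**The case against.** The strongest defence is that a single generic model for a long list of secondary measures is common and valid. The protocol treats secondary outcomes separately throughout, down to a different significance level, and the extra covariates were specified only for the co-primary model. It also defers full analysis details to an SAP. Most of this stands: the planned 52-week analysis is valid, and no power target is attached to it. Deferral does not remove the mismatch, however, because the covariate lists are already written down and differ without explanation.

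A reader might go further than the text allows in three ways:

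- **That differences between the analyses could not be attributed to time or to missing data.** The swap between complete-case analysis and multiple imputation tests missing data with no stated covariate change. The mixed model holds all visits under one covariate set, so 27 and 52 weeks can be compared there, given an arm-by-time term (not stated, but ordinary SAP detail).
- **That the 52-week estimate is biased.** For a continuous score with an identity link under randomisation, each model targets the same mean difference.
- **That the therapist model also drops prior CBT.** The protocol describes it as adding a random effect, most naturally to the primary model, which already carries prior CBT.

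**Conclusion.** The inconsistency is real and stated: three covariate sets for one outcome, with no reason given. Its effect is small. There is no bias under randomisation and no effect on the sample size. At 52 weeks the loss is about 1% to 4% in standard error, or roughly 0.4 to 1.5 percentage points of power. That size rests on an assumed 2% to 8% of residual variance explained, and on carrying the 27-week SD, correlation and number analysed to 52 weeks. If the omitted covariates explain nothing, nothing is lost.

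The mismatch also adds avoidable chance variation when the 27-week ANCOVA is read against the 52-week or mixed-model result. It alters the mixed model's missing-at-random condition only if prior CBT predicts dropout. This is a minor improvement worth making because it is free; it is not a flaw that threatens a conclusion.

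**What to change.** In Protocol section 8, and in the SAP to match:

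- **Secondary outcomes:** for LIFE depression and mania PSR at weeks 17 and 52, adjust for site, BAR group, both baseline PSRs and prior CBT, as in the 27-week ANCOVA. The generic rule can stay for the other secondary measures.
- **Sensitivity analysis:** add prior CBT to the longitudinal mixed model.
- If a difference is intended, state the reason.

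The therapist model and the missing-data swap need no change. The cost is about one sentence, with no new data: two degrees of freedom in the week 17 and week 52 models, and one in the mixed model if prior CBT enters as a main effect. It should be settled before database lock.

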9. DATA MANAGEMENT

Data management will ensure each study participant is assigned a unique trial identification number at the start of assessments and written on all clinical assessment forms/datasheets and databases used to record data on study participants. A record sheet linking patient identity, contact details and trial identification number for all participants is kept at each site. It will be placed securely in a locked filling cabinet separate from datasheets. This will be stored in an electronic database, accessible only to authorised users at the sites via the study web portal hosted at York CTU (password protected and secure). The local study co-ordinator will enter the data on to a REDCap Cloud database, and managed and subject to quality control according to MCTU procedures by MCTU.

Data will be held securely on a cloud-hosted REDCap server. Access to the study interface will be restricted to named authorised individuals granted user rights by a REDCap administrator at York CTU. All data will be kept secure at all times and maintained in accordance with the requirements of GDPR and archived according to GCP regulations. Paper data collection forms transferred to or from the York Clinical Trials Unit will be coded with a study number, the participant's initials, and date of birth. Data will be held securely on paper and electronically at York Clinical Trials Unit and appropriate processes put in place for the transfer, storage, restricted access, and disposal of personal information. Relevant Standard Operating Procedures, Guidelines, and Work Instructions in relation to data management, processing, and analysis of data will be followed.

Participating sites will be expected to maintain a file of essential trial documentation (Investigator Site File), which will be provided by GMMH and keep copies of all completed paper assessment packs and consent forms for the trial securely.

10. MONITORING, AUDIT & INSPECTION

Each site will have a weekly team meeting to ensure regular communication and interaction between site leads, local clinicians and research assistants (with measures to maintain the blind). Monthly Trial Management Group meetings with all applicants via video conference will occur, with 6 monthly extended meetings. LP will conduct weekly telephone supervision with all RAs focusing on recruitment, liaison with referrers, compliance to follow-ups, and specific scoring queries for interview-based measures. In addition, LP will chair a fortnightly teleconference focusing on inter-rater reliability of the interview measure and recruitment to share best practice. Therapists receive weekly site supervision from a central supervisor based in Manchester, focused on fidelity and adherence to the protocol and manual. Line management / supervision from site leads focussed on problem solving, personal wellbeing, risk management and local issues will supplement this. Quarterly triadic site supervision involving supervisee, central supervisor and site leads will be used to ensure these

arrangements operate smoothly. We have used these processes successfully in several previous multisite RCTs of psychosocial interventions [99, 100].

Data will be monitored for completeness by the research assistants at the end of each visit. Researchers may also contact participants by telephone or e-mail to facilitate data completion where appropriate.

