Participants will receive a £20 payment upon completion of the baseline and each follow-up appointment at 17-, 27-, and 52-weeks (£80 in total). In addition, a 39-week check in phone call will be conducted with each participant to confirm that contact details remain the same.

THE RANDOMISATION SCHEME

Eligibility will be confirmed via completion of the eligibility review form following the baseline assessment. This will be completed at an eligibility supervision between the research assistant and a supervisor (central site supervisor e.g. CI or trial manager, or local site lead or PI with delegated responsibility). The outcome of the eligibility review form will then need to be entered onto REDCap within 2 working days of completion of the review. If the person is eligible, randomisation will be undertaken automatically once entered in REDCap. Participants will be randomised to one of two trial arms (CBT_{BAR} + TAU **or** TAU alone). Randomisation will be independent and concealed, using permuted stratified blocks (using site and BAR Group*), via a web-based system at York Clinical Trials Unit.

*Confirmed BAR Group will be based on hierarchical rule system. Group 1 will be the stratification grouping for any participants meeting Group 1 and another BAR group (e.g. meets criteria for BAR Group 1 and 2). Group 2 will be the stratification grouping for any participants that meet BAR Group 2 and 3).

METHOD OF IMPLEMENTING THE RANDOMISATION/ALLOCATION SEQUENCE

The allocation is made known to the trial manager (to monitor adherence to the randomisation algorithm), the local trial administrator, local PI or site lead, and local trial therapist(s) by email and SMS text message. The allocation is made known to the participant by letter from the local trial administrator. Blinding of the allocation code will be maintained for research assistants.

BLINDING

Single blind – assessors will be blind to treatment condition. Blindness will be maintained using a wide range of measures which we have implemented successfully in other single blind trials within our trust research departments. These include separate offices for the therapists and research assistants, protocols for answering telephones including reminders for clinicians, participants and family members about the blind, protocols for message taking and secretarial support, separate diaries and pigeon holes and data file security, using passwords and encryption of randomisation information.

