We will develop a standard operating procedure (SOP) for maintaining, recording, and managing blinding, which will outline all of these procedures. This SOP will be reviewed by, and agreed with, our DMEC and TSC. Each researcher will sign this SOP to confirm they understand and will comply with the blinding procedures. All blind breaks will be recorded by the trial manager and reviewed by the Chief Investigator for patterns in unblindings and be reported to the TSC and DMEC. There is only one follow-up scheduled during the intervention window (at 17-weeks). This will reduce the risk of blind breaks occurring because of therapists and RAs crossing paths for visits and it will reduce the opportunity for unblinding to occur because of communication with participants to arrange visits. Our qualitative researcher WJ will be conducting interviews with participants who have received the CBT_{BAR} intervention, and this poses an unblinding risk if the RAs learn which participants met with WJ. All interviews for the qualitative research by WJ with the participants will occur at a timepoint away from a standard follow-up point and will be overseen by the trial manager to ensure participants and the RA's are not in contact.

Maintaining rater blindness to treatment allocation is crucial. Following eligibility assessment and completion of baseline assessments, participants will be allocated to treatment groups through our web-based randomisation service and the Trial administrator will inform the participants of this decision. All letters to participants and clinicians will contain a standardised statement about the need to maintain the single blinding process. Any accidental unblindings will be recorded. Where possible, we will identify an independent assessor with whom the blinding has not been broken to complete subsequent follow-ups, subject to any threats to participant engagement with follow-up.

TRIAL ASSESSMENTS

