Following the recruitment process, baseline assessment and randomisation, follow-up assessment points will be at 17-, 27-, and 52-weeks post-randomisation (see "Schedule of Events" in the Appendices (#2)). We will also contact people via telephone at 39-weeks to promote retention in the trial and ask about general wellbeing since the last assessment (including documenting any potential serious adverse events, and any changes to contact details). Assessments will be conducted by research assistants blind and independent to treatment group and will employ both a semi-structured interview to gather data for the primary outcome (blinded) and secondary outcomes in addition to self-report questionnaires (unblinded data given the participant will be aware of their treatment allocation). The self-report questionnaires will be offered for completion in paper format.

For those participants who are offered the CBT_{BAR} intervention, a measure of therapeutic alliance (California Psychotherapy Alliance Scales / CALPAS) will be administered to both the participant and the therapist for completion after the 4th and 10th sessions. To ensure the participant is able to complete the measure openly, the trial manager (LP) will be responsible for contacting the participant and arranging administration of this measure to prevent the therapist being the person to do this. Additionally, the Facilitative Alliance Measure will be administered by the trial manager (LP) to the research participants following each follow-up appointment with a research assistant. This will measure alliance with the research assistant.

Follow-up visits are typically offered via face-to-face methods utilising outreach principles where participants are seen in non-stigmatising settings. This approach means that people often choose to be seen at home although other least restrictive venues e.g. youth centres, colleges, primary care settings, are also employed. Staff training will be conducted with all staff and regular arrangements for ensuring inter-reliability across sites. Adapting to assessments via phone/virtual calls still retains validity and reliability on our primary outcome [84].

QUALITATIVE RESEARCH

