A participant is free to withdraw from the trial at any point if they wish to do so, without giving a reason and without it affecting their care. If a patient withdraws consent to participate, clarification will be sought on whether withdrawal is from the intervention component (CBT_{BAR}), and/or completing the assessments (clarifying if this includes both or either the semi-structured interviews and the self-report measures). A participant who chooses to withdraw from an intervention arm will be encouraged to continue with research assessments if they are happy to do so.

Withdrawal can also include the clinical decision by the trial therapist at site to cease or alter trial treatment, and potentially withdraw the patient from treatment. Examples of why this might be completed could include loss of capacity to consent or significant change to the person's circumstances such as significant issues with drugs or alcohol. This would be classed as "Treatment Discontinuation" on the withdrawal form. Clarification would be needed by the clinician if the research team should continue to contact the participant as normal at the follow-up points.

For those participants who take part in the nested qualitative study, they will be free to withdraw from this as well. The qualitative study will be a one-off qualitative interview; however, it could be the person initially agrees to take part but does not finish the interview. Or the person later seeks to withdraw their interview from use in the analysis.

Data collected up to the date of withdrawal of consent will be used in the analyses unless the person requests the data is not used. If necessary or helpful, an unblinded member of the research team (e.g. trial manager) will aim to have a discussion with the participant regarding their wishes.

The information about the withdrawal will be captured on a withdrawal form at site and entered onto REDCap.

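### The lead-site trial manager who arranges the CBT-only alliance measure also advises the blinded raters on scoring, and no stated safeguard covers that route to the co-primary ratings

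*Protocol*

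**What the plan says.** On blinding, the Protocol sets its own standard in section 5 (Blinding): "Maintaining rater blindness to treatment allocation is crucial". The allocation subsection just before it says "Blinding of the allocation code will be maintained for research assistants".

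On the trial manager's knowledge of allocation:
- Section 5 (Method of Implementing the Randomisation/Allocation Sequence): "The allocation is made known to the trial manager (to monitor adherence to the randomisation algorithm".
- Section 5 (Withdrawal Criteria) gives, as someone who may talk to a withdrawing participant, "an unblinded member of the research team (e.g. trial manager".
- Section 5 (Trial Assessments) describes the CALPAS thus: "For those participants who are offered the CBT_{BAR} intervention, a measure of therapeutic alliance". It is completed after sessions 4 and 10. The trial manager, here identified by initials, "will be responsible for contacting the participant and arranging administration of this measure to prevent the therapist being the person to do this".

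On the trial manager's contact with raters, section 10 uses the same initials for the person who conducts "weekly telephone supervision with all RAs focusing on recruitment, liaison with referrers, compliance to follow-ups, and specific scoring queries for interview-based measures" and who chairs a "fortnightly teleconference focusing on inter-rater reliability of the interview measure". Section vi (Trial Steering Committee) attaches these initials to the lead-site trial manager.

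**The concern.** Participants and therapists know the arm, so blind rating is the main defence of the co-primary outcomes against detection bias. Both outcomes are Psychiatric Status Ratings from a semi-structured interview, where borderline weeks call for judgement and raters can be expected to seek advice. If the adviser knows the participant's arm, the advice can lean with that knowledge even though the rater stays blind. Nothing would then appear in the blind-break log, because the rater has learned nothing about allocation. Ratings influenced in this way cannot be repaired in the analysis.

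**Working it through.** **Step 1: is it one person?** Section vi, section 5 (Trial Assessments) and section 10 use the same initials, and the first two attach the trial manager title to them. The CALPAS duty and the scoring supervision therefore fall to one role-holder.

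**Step 2: does that person learn the arm?** The CALPAS is given only in the CBT arm, so arranging it shows who is in that arm. Sessions are weekly, so sessions 4 and 10 would normally fall well before the week-27 rating. In the feasibility trial 32 of 37 CBT participants (86%) attended at least 6 sessions (section 6), so most would reach session 4. Two other duties assigned to the trial manager by title point the same way (section 5, Blinding): recording all blind breaks, and overseeing the qualitative interviews with people who received the therapy.

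**Step 3: does the advice reach the co-primary outcomes?** Section 10 refers to interview-based measures without naming one. The SCID LIFE interview supplies both co-primary outcomes (section 8), and section 5 (Trial Assessments) says research assistants rate it blind. Queries about baseline ratings arise before randomisation and carry no risk. Those from weeks 17, 27 and 52 do.

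**Step 4: does a stated safeguard cover it?** Section 3 (Main Trial) and section 5 (Blinding) list separate offices and diaries, telephone and message protocols, secured randomisation information, a signed SOP, logging of blind breaks and, where possible, a replacement assessor. These keep raters away from therapists and allocation data. None concerns scoring advice. In section 10 the qualifier about protecting the blind is attached to the weekly site meeting, not to the scoring supervision or the reliability call.

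**Step 5: scale, by assumption only.** Inputs from section 3 (Sample Size): SD 1.3, baseline correlation 0.4, 286 analysed (143 per arm), two-sided alpha 2.5%, target difference 0.5.

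The plan's own figure reproduces. The ANCOVA SD is 1.3 × √(1 − 0.4²) = 1.191. The number per arm is 2 × (2.241 + 1.282)² × 1.191² / 0.5² ≈ 141, or 282 in total against the stated 286. Power at 143 per arm is 90.4%. The sample size is not in question.

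Standard error of the arm difference: 1.3 × √0.84 × √(4/286) = 0.141.

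For a differential rating shift b with no true effect, type I error = P(Z > 2.241 − b/SE) + P(Z < −2.241 − b/SE).

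| Assumed shift b (LIFE depression) | b/SE | Type I error |
|---|---|---|
| 0 | 0 | 2.5% |
| 0.05 | 0.35 | 3.4% |
| 0.10 | 0.71 | 6.4% |
| 0.20 | 1.42 | 21% |

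A shift of 0.10 would arise, for example, if 20% of week-27 interviews raised a query and advice moved those ratings by 0.5 in one arm only (0.20 × 0.5). A shift of 0.20 needs the same movement in opposite directions in the two arms.

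For LIFE mania (SD 0.5 from section 3; correlation 0.4 assumed here), SE = 0.5 × √0.84 × √(4/286) = 0.054. Shifts of 0.025 and 0.05 give about 4.1% and 9.4%.

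**The case against.** The strongest reply is that the Protocol describes supervision, not adjudication. Section 10 lists scoring queries as one of four topics and gives the supervisor no power to approve or change a rating. A reader might infer that this person settles borderline scores; no text says so. A reader might also infer that rater blinding itself is broken. It is not: the research assistants stay blind, and the exposure is limited to influence through advice.

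A further tempting inference is that this person is sent every allocation. Section 5 notifies the trial manager in the singular, while section vi (Trial Management Group) lists two lead-site trial managers and one at York CTU. The stated purpose, checking adherence to the randomisation algorithm, could fit the CTU post. Receipt of all allocations is therefore probable for this person, but not proven. The CALPAS route does not depend on it, although it reveals only the CBT participants for whom the measure is arranged.

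Finally, the blinding measures are introduced as examples, and the blinding SOP, to be agreed with the DMEC and TSC, could require anonymous queries. That is possible. But the Protocol describes the SOP as setting out the procedures it has just listed, and scoring advice is not among them. Anonymity would also need care, because the same supervision covers follow-up compliance and the same person administers the assessor alliance measure after follow-up visits, so participants may be recognisable.

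These points narrow the concern. They do not remove the overlap of duties or supply a safeguard for it.

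**Conclusion.** The concern holds as a risk of detection bias in both co-primary outcomes, confined to scoring advice given after randomisation. It rests on two facts in the text (one role-holder for the CALPAS and for scoring supervision; no stated safeguard on that route) and on one inference, that advice on a specific query can affect the rating given.

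The size is unknown. The Protocol gives neither a query rate nor any measure of how far advice moves a rating, and the range should be read from zero upward. The 6.4% and 21% figures show how sensitive a 2.5% test is to small systematic shifts; they are not estimates of what will happen. The sample size and the analysis model are unaffected.

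**What to change.** Assign post-randomisation scoring queries and the reliability calls to an existing team member who receives no allocations and has no part in CALPAS contact, oversight of the qualitative interviews, blind-break recording or withdrawal discussions. Moving the CALPAS alone would leave the other routes to allocation open.

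One of the two lead-site trial managers could take the blinded role and the other the unblinding duties, with the notification list in section 5 naming which manager is told. A site lead would not be suitable, because section 5 also notifies site leads of allocations. If the separation is not feasible, require queries to be submitted de-identified.

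State the rule in section 5 (allocation sequence, Blinding, Trial Assessments, Withdrawal Criteria), in section 10 and in the blinding SOP. The cost is a reallocation of tasks among existing staff, a change to the notification list and some wording.
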